13.1 Primary Endpoint

- The rate of AE's/SAE's related to Tice® BCG administration reported at any point during the study,
- Summary of the distribution of viable BCG bacteria from intradermal challenge sites at 4 time points (approximately 3 days and 1, 2, and 4 weeks following Tice® BCG administration), as detected by quantitative CFU plating. The distribution will be summarized in terms of its central tendency (mean or GM) and its precision represented by the appropriate 95% confidence interval.

13.2 Secondary Endpoint

- Quantitative bacterial 16S ribosomal DNA PCR,
- Microbial viability testing pre-ribosomal RNA RT-PCR,
- Humoral and cellular immune responses after BCG immunization.

14.0 SUBJECT DISCONTINUATION OF ACTIVE TREATMENT

Subjects may voluntarily withdraw their consent for study participation at any time and for any reason, without penalty.

A subject may be withdrawn from the study for the following reasons:

- The subject withdraws consent,
- The subject develops a medical disease or condition, or any new clinical findings for which continued participation, in the opinion of the site principal investigator or appropriate sub-investigator, would compromise the safety of the subject, would interfere with the subject's successful completion of this study, or would interfere with the evaluation of responses,
- The subject fails to comply with the scheduled study visits,
- The study is terminated,
- Any reason that, in the opinion of the investigator, precludes the subject's continued participation in the study,
- The subject becomes pregnant.

15.0 ASSESSMENT OF SAFETY

15.1 Specification of Safety Parameters

Safety will be assessed by the frequency and severity of:

1. Tice® BCG-related serious adverse events occurring throughout the course of the study,
2. Solicited Adverse Events – reactogenicity events following Tice® BCG administration:
 - a) Local reactions including pain, tenderness, erythema/redness, and induration/swelling at the injection site.
 - b) Systemic reactions including fever, chills, malaise/fatigue, headache, night sweats, nausea, vomiting, diarrhea, rhinorrhea, cough, and wheezing or shortness of breath.
3. Lesion characterized as erythematous macule, non-erythematous papule, erythematous papule, vesicle, pustule, ulcer, eschar/crust, healed, scar, or keloid,
4. Lymphadenopathy,
5. Clinical safety laboratory adverse events to include WBC, hemoglobin, and platelet count, creatinine and ALT (SGPT),
6. Unsolicited Adverse Events.
 - a) Non-serious adverse events occurring in the 56 days following Tice® BCG administration.

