5.8 Potential Risks and Benefits

5.8.1 Known Potential Risks

Risks of BCG

The BCG vaccine continues to be the most widely distributed vaccine worldwide, generally provided to infants immediately after birth, so it is safe and well tolerated. Typically, most people will develop a small swelling (nodule) at the injection site that break open, release pus or blood-tinged discharge, and form an ulcer the size of a dime. The ulcer will heal over a period of weeks and forms a scar that remains for life. Occasionally, lymph nodes around the vaccination site can become tender to touch. “Flu-like” symptoms that are common to many vaccines includes fevers, chills, loss of appetite, muscle aches, and generally not feeling well can last 1-2 days.

A very small number of people (1 in 4 million) have an immediate allergic reaction to BCG. Symptoms include rash, swelling around the mouth, difficulty breathing. These can be treated with emergency medications. If severe, they can cause death.

There is a risk that by receiving the BCG vaccine, participants may develop a false positive tuberculin skin test (PPD) that will complicate the early diagnosis and treatment of latent (inactive) TB. However, a diagnosis of latent TB can be confirmed by other methods, including a clinical examination, chest x-ray, and blood test (IFN-g release assay).

Risks of Isoniazid (INH)

Participants who are administered Isoniazid may experience some side effects that include: numbness and tingling in the extremities, hepatitis (symptoms include loss of appetite, nausea, vomiting, fatigue, malaise, and weakness), nausea, vomiting, upset stomach, fever, and rash.

Participants will be closely monitored by study staff and necessary treatment will be administered to alleviate symptoms that may occur.

Risks of Intradermal Injection

Participants may experience: pain, swelling, redness, itching caused by the ID injection. There is potential for an infection at the ID challenge site.

Risks of Skin Biopsy

Participants may experience: pain, swelling, redness, bleeding and bruising at the biopsy site during and a day or two after, damage to the skin such as artery or nerve and possible scarring. There is potential for an infection at biopsy site or allergic reaction to the anesthetic or gel foam

used to close the biopsy site. Participants cannot swim in a chlorinated water until the gel foam has sufficiently closed the biopsy area.

Risks of Blood Draws

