6.0 OVERVIEW OF CLINICAL TRIAL

6.1 Study Objectives

6.1.1 *Primary Objectives*

- Evaluate the safety and tolerability of Intradermal Tice® BCG followed by a short course (3 days) of isoniazid (INH).
- Assess the BCG bacterial burden in skin biopsies as measured by culture.

6.1.2 *Secondary Objectives*

- Assess the BCG bacterial burden in skin biopsies as measured by a novel qPCR assay.
- Evaluate peripheral blood cellular frequencies (Trucount) after intradermal BCG.
- Evaluate adaptive immune response after intradermal BCG (validated intracellular cytokine staining after stimulation).

6.1.3 *Exploratory Objectives*

- To conduct analyses related to furthering the understanding of TB, immunology, vaccines, and clinical trial conduct.

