15.2.2 Reactogenicity

Reactogenicity events are AEs that are known to occur with Tice® BCG. Reactogenicity events will be analyzed according to the following grading scales:

Table 1: Reactogenicity Events Grading Scales

Local Reaction	Mild (Grade 1)	Moderate (Grade 2)	Severe (Grade 3)
Pain – experienced without touching the injection site	Subject is aware of pain but it does not interfere with daily activity and no pain medication is taken	Subject is aware of pain; there is interference with daily activity or it requires use of pain medication	Subject is aware of pain and it prevents daily activity
Tenderness – hurts only when injection site is touched	The area immediately surrounding the injection site hurts only when touched and it does not	The area immediately surrounding the injection site hurts when touched and it interferes with daily activity	The area immediately surrounding the injection site hurts when touched and it prevents daily activity

	interfere with daily activity		
Erythema/Redness*	Does not interfere with activity	Interferes with activity	Prevents daily activity
Induration/Swelling*	Does not interfere with activity	Interferes with activity	Prevents daily activity
Drainage	Continuous use of bandage cover or less than 2, 2x2 gauze pads/day	Needs 2-4, 2x2 gauze pads/day	Needs more than 4, 2x2 gauze pads/day

* Will be also measured in mm but size will not be used as halting criteria.

Erythema/redness, induration/swelling and lesion as analyzed by measurement will be graded as follows:

Table 2: Erythema/Redness, Induration/Swelling and Lesion Measurement Grading Scales

	Small	Medium	Large
Total Erythema/Redness*	<20 mm	20-50 mm	>50 mm
Maximum Diameter of Induration/Swelling*	<20 mm	20-50 mm	>50 mm
Central Lesion	<10 mm	10-30 mm	>30 mm

* Measurement will not be used as halting criteria

Table 3: Reactogenicity Events Grading Scales (Continued)

Systemic (Subjective)	Mild (Grade 1)	Moderate (Grade 2)	Severe (Grade 3)
Chills	No interference with activity	Some interference with activity	Significant interference, prevents daily activity
Malaise/Fatigue	No interference with activity	Some interference with activity	Significant interference, prevents daily activity
Headache	No interference with activity	Some interference with activity	Significant interference, prevents daily activity
Night Sweats	No interference with activity	Some interference with activity	Significant interference, prevents daily activity

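### The solicited symptom list leaves out two of the five systemic BCG effects the protocol names and several of its named isoniazid effects, so these are ascertained less systematically, though not lost

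*Combined protocol and SAP*

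**What the plan says.** Section 15.1 introduces item 2 as "Solicited Adverse Events – reactogenicity events following Tice® BCG administration". Item 2b then lists the systemic ones: "Systemic reactions including fever, chills, malaise/fatigue, headache, night sweats, nausea, vomiting, diarrhea, rhinorrhea, cough, and wheezing or shortness of breath". Section 15.2.2 gives the principle behind such a list: "Reactogenicity events are AEs that are known to occur with Tice® BCG". Table 3 grades every item in 2b except fever, which Table 4 grades.

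Section 5.8.1 describes what is expected after each product. For BCG, the flu-like symptoms are "fevers, chills, loss of appetite, muscle aches, and generally not feeling well can last 1-2 days". For INH, the effects are "numbness and tingling in the extremities, hepatitis (symptoms include loss of appetite, nausea, vomiting, fatigue, malaise, and weakness), nausea, vomiting, upset stomach, fever, and rash".

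Section 6.1.1 makes safety and tolerability of the sequence, BCG and then three days of INH, the first primary objective. No solicited list is tied to INH.

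Events outside the list have their own route. Section 15.2.1 has all AEs on study documented regardless of relationship, and gives a generic three-grade scale for events the tables do not cover. Section 15.1 (item 6a) collects non-serious unsolicited events for 56 days after BCG. Appendix B shows an AE review at every visit from 2 to 17.

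**The concern.** By the protocol's own definition, the effects it names for BCG should be the ones it solicits. Two are missing. The objective also concerns a two-product sequence, while the checklist is built around one product, so some effects the protocol attributes to INH are not asked about by name.

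A symptom that is asked about and one that is left to be volunteered are not measured in the same way. With five participants per arm, one unreported symptom is 1/5 = 20% of an arm. The trial is open label with an untreated control, so what people volunteer may depend on knowing their group. Identical questions in both arms are the simple protection.

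Other INH-directed measurement is limited. The endpoint in section 13.1 is worded as "The rate of AE's/SAE's related to Tice® BCG administration reported at any point during the study", and section 10.6.4 and Appendix A schedule ALT at screening only, with later tests discretionary. Symptom questions therefore carry much of the weight for INH tolerability.

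**Working it through.** **Step 1: BCG effects in section 5.8.1 against item 2b and Tables 3 and 4.** I read generally not feeling well as malaise.

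| Named for BCG | Solicited and graded? |
|---|---|
| Fever | Yes (Table 4) |
| Chills | Yes (Table 3) |
| Not feeling well | Yes, as malaise/fatigue (Table 3) |
| Loss of appetite | No |
| Muscle aches | No |

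Result: 3 of 5 solicited, 2 of 5 (40%) not.

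**Step 2: INH effects in section 5.8.1 against the same list.** Hepatitis is represented by the symptoms given for it, and each distinct symptom is counted once.

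| Named for INH | Solicited? |
|---|---|
| Nausea, vomiting, fatigue, malaise, fever | Yes |
| Numbness, tingling, rash, upset stomach, weakness, loss of appetite | No |

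Result: 5 of 11 solicited, 6 of 11 not (five entries if numbness and tingling count as one). The matching is term by term. A reader who treats upset stomach as covered by nausea, or weakness as covered by malaise/fatigue, would shorten the list. Numbness/tingling and rash have no near equivalent in it.

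**Step 3: grading.** Table 3 reserves Grade 3 for significant interference that prevents daily activity. The generic scale in section 15.2.1 assigns Grade 3 to events that interrupt usual activity and brings treatment into the definition. The two scales are close but not identical, so a headache and a muscle ache of equal impact could be graded under different wording.

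**Step 4: the plan's own detection figures.** Section 18.1 gives, for a true rate of 25% in five participants, 0.76 for at least one event and 0.37 for at least two.

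- Pr(≥1) = 1 − 0.75^5 = 1 − 0.237 = 0.763
- Pr(≥2) = 1 − 0.75^5 − 5 × 0.25 × 0.75^4 = 0.367

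Both reproduce. They assume that every event is recorded.

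**Step 5: illustration only.** The documents give no capture rate. If a symptom with a true rate of 25% is recorded with an assumed probability c, then Pr(≥1 of 5) = 1 − (1 − 0.25c)^5.

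| Assumed c | Pr(≥1 of 5) |
|---|---|
| 1.00 | 0.76 |
| 0.75 | 0.65 |
| 0.50 | 0.49 |
| 0.25 | 0.28 |

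This shows how sensitive the section 18.1 figure is to incomplete capture. It does not estimate what will happen in this trial.

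**The case against.** The strongest reply is that nothing is lost. Participants are told to record unsolicited events, staff review AEs at every visit from 2 to 17, and clinic visits fall on each of Days 0 to 6 and on Day 8±1. That covers the three INH days and the early period of a BCG reaction said to last 1-2 days. The 56-day window covers them too, the generic scale supplies a grade, and the endpoint in section 13.1 counts events whether solicited or not. All of this stands, and it limits the point to uniformity of ascertainment and grading.

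Item 2b also says *including*, so it is formally open. Item 2a omits drainage, which Table 1 nevertheless grades, so the section 15.1 lists are not exhaustive. That is fair, but no table has a row for muscle aches or loss of appetite. Section 10.6.2 illustrates unsolicited events only with local ones. The survey itself is not in the documents and may contain more.

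Nor is it a fault that rhinorrhea, cough and wheezing are solicited. Every solicited systemic item also appears in the pre-BCG symptom check of exclusion criterion 2 and so has a baseline. The items proposed here are not named in that check, although abdominal pain comes close to upset stomach. Any addition has to deal with this.

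A reader might infer that all INH symptoms are missed. The documents do not support that: nausea, vomiting, malaise/fatigue and fever are INH effects in section 5.8.1 and are solicited.

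**Conclusion.** The point holds as an internal mismatch with a cheap remedy. Two of the five systemic BCG effects in section 5.8.1 are outside the solicited list and its grading tables, against the definition in section 15.2.2. Six of the 11 distinct INH symptoms are also unlisted, although the first primary objective covers BCG followed by INH. The consequence is less systematic ascertainment and slightly different grading wording for these symptoms. The counts rest on term-by-term matching and on the survey following item 2b.

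A reader might go further and infer that the design biases the trial towards finding BCG plus INH as well tolerated as BCG alone. The documents do not support that. Section 18.1 presents safety descriptively, says the study is not powered to compare the groups, and states no such target conclusion. Direction is also open, because participants who know they took INH may volunteer INH symptoms more readily. Neither the size nor the direction of an effect on the arm comparison can be derived, since no capture rates are given.

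**What to change.** 1. Add muscle aches and loss of appetite to section 15.1 (item 2b), Table 3 and the REDCap survey, using the existing activity-interference grades.
2. Add numbness/tingling, rash, upset stomach and weakness as solicited items, asked in the same words in both arms over the same days. Tabulate them separately from BCG reactogenicity. Loss of appetite, named for both products, is covered by the first change.
3. Record whether each added symptom is present before BCG, because exclusion criterion 2 does not supply that baseline.

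If the list is deliberately kept short, state in section 15.1 that the remaining effects in section 5.8.1 are captured as unsolicited AEs, and why. That removes the inconsistency but not the difference in ascertainment.

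The cost is six survey lines with their grading rows, a short baseline question, slightly more diary burden and somewhat higher reported reaction rates. The sample size and the figures in section 18.1 do not change.

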10.6.4 Laboratory Evaluations/Assays

Whole blood samples will be collected via venipuncture for clinical safety laboratory evaluations and BCG response assays. A total of ~730mls (~3 cups) will be drawn for the entire study. At the screening visit (visit 1) and Days 0 (visit 2), 1 (visit 3), 2 (visit 4), 3 (visit 5), 4 (visit 6), 8 ± 1 (visit 7), 15 ± 1 (visit 8), 28 ± 1 (visit 9), 56 ± 2 (visit 10), 84 ± 3 (visit 11), 98 ± 1 (visit 12), 112 ± 1 (visit 14), and 114 ± 1 (visit 15), these standard blood draws will be collected from each participant to perform immunogenicity and humoral assays.

Clinical safety assessments

Blood samples for clinical safety laboratory evaluations (WBC, hemoglobin, platelet count, ALT (SGPT), creatinine) will be collected from each subject prior to administration of Tice® BCG at the screening visit (visit 1). These parameters must meet protocol-defined eligibility criteria to be enrolled and receive Tice® BCG. Additional clinical safety laboratory evaluations may be deemed necessary during the study.

Measuring BCG response

Skin biopsy (via XX)

Skin biopsies will be taken to quantify BCG bacteria. The ID challenge site will be biopsied on Days 3, 8, 15 and 56 (visits 5, 9, 10, and 12) after Tice® BCG administration. A 4mm skin biopsy using the punch method will be taken at the ID challenge site. A local anesthetic injection will be given to numb the site. Gel foam will be used to close the biopsy area. A medically licensed research team member will perform the biopsy.

The number of viable BCG bacteria will be measured on Day 3 from the skin biopsy by 1) quantitative CFU plating, 2) the numbers of genomes of BCG by quantitative real time PCR, and if sufficient material is available, by 3) additional assays may be performed to assess the integrity of the immune system.

Blood samples (via venipuncture)

- Serum will be collected on Days: 0, 1, 2, 3, 4, 8 ± 1 , 15 ± 1 , 28 ± 1 56 ± 2 , and 84 ± 3 , scheduled visits will be collected for inflammatory markers (IL-2, IL-4, IL-5, IL-8, IL-10, INF γ , 1L-12p70, 1L-17A, IL-1, IL-6 and TNF- α levels) using Cytokine BeadArray, and clinical testing for acute phase reactants (ESR and CRP).

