15.2 Methods and Timing for Assessing, Recording, and Analyzing Safety Parameters

15.2.1 Adverse Events

Adverse Event (AE):

International Conference on Harmonisation (ICH) E6 defines an AE as any untoward medical occurrence in a patient or clinical investigation subject administered a pharmaceutical product regardless of its causal relationship to the study treatment. An AE can therefore be any unfavorable and unintended sign (including an abnormal laboratory finding), symptom, or disease temporally associated with the use of a medicinal (investigational) product. The occurrence of an AE may come to the attention of study personnel during study visits and interviews of a study treatment recipient presenting for medical care, or upon review by a study monitor.

All AEs, including local and systemic reactions, not meeting the protocol-defined criteria for serious adverse events (SAEs) should be captured on the appropriate data collection form and eCRF. Information to be collected for unsolicited AEs includes event description, date of onset, study clinician's assessment of severity and relationship to study product and alternate etiology (if not related to study product) (assessed only by those with the training and authority to make a diagnosis), date of resolution/stabilization of the event, seriousness and outcome. All AEs occurring while on study will be documented appropriately regardless of relationship. All AEs will be followed to adequate resolution.

Any medical condition that is present at the time that the subject is screened should be considered as baseline and not reported as an AE. However, if the severity of any pre-existing medical condition increases at any time during the study, it should be recorded as an AE.

All AEs must be graded for severity and assessed for relationship to study product (see definitions below). Adverse events characterized as intermittent require documentation of onset and duration of each episode. The start and stop date of each reported AE will be recorded on the appropriate data collection form and eCRF.

Severity of Event:

All AEs will be assessed by the site principal investigator or appropriate sub-investigator using the protocol-defined grading system (Section 15.2.2-15.2.3). For events not included in the protocol defined grading system, the following guidelines will be used to quantify severity:

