18.1 Sample Size and Power for Outcome Measures

The study is designed to demonstrate the safety, tolerability and feasibility of using intradermal BCG as a model for the evaluation of TB drugs. With 5 participants in each arm and a low number of AE/SAEs expected, the study is not powered for direct comparison of the two study groups. Instead, reactogenicity, AEs and SAEs will be presented with descriptive statistics summarizing each group. Interpretation of differences will rely heavily upon clinical judgment. In the rare event that there is a high frequency safety event of at least 25% in one of the groups there will be a 76% chance of observing at least one event and a 37% chance of observing 2 events in the relevant group. All participants are expected to provide safety data.

True event rate (%)	Pr(0/5)	Pr(≥1/5)	Pr(≥2/5)
5	0.77	0.23	0.02

10	0.59	0.41	0.08
15	0.44	0.56	0.16
20	0.33	0.67	0.26
25	0.24	0.76	0.37

It is expected that BCG will be detectable in all skin biopsies provided 4 days after BCG immunization and that the 3 day INH treatment will eliminate detectable BCG in all participants. Therefore, even with only 5 participants per group there will be power to detect a difference in the number of participants with detectable BCG either by qPCR or culture. The plot below shows that a low rate of BCG detection in the treatment arm (<0.05) and a high rate of detection in the control arm (>0.95) there will be >90% power to detect a difference between the groups (Fisher's exact test, two-sided $\alpha=0.05$). Power will be diminished if the actual detection rates are shifted toward 0.5 for either group. It is assumed all participants will contribute data for this objective.

Descriptive statistical analyses will be conducted with the data generated from the Secondary Endpoints. The analyses will generate hypotheses to be tested in future studies.

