22.0 APPENDICES

Appendix A: Lab Procedures Table

Procedure	Ship to	Tube	Tube size (vol. capacity)	Tube volume (mL)																	Total			
				Visit:		1	2	3	4	5	6	7	8	9	10	11	12	13	14	15				
				Day:		Screening visit	D0	D1	D2	D3	D4	D5	D6	D8	D15	D28	D56	D84	D98	D100				
				Week:		W0	W0	W0	W0	W0	W0	W0	W1	W2	W4	W8	W12	W14	W16	W16				
				BCG		—	—	—	—	Biopsy	INH	INH	INH	—	—	—	—	—	—	—				
BLOOD COLLECTION																								
Screening or diagnostic assays																								
IGRA	Local Lab	Local Lab	EDTA	5mL	4	—	—	—	—	—	—	—	—	—	—	—	—	—	4	—	4			
Screening HIV test	Local Lab	Local Lab	EDTA	5mL	5	—	—	—	—	—	—	—	—	—	—	—	—	—	—	—	5			
HBsAg/anti-HCV	Local Lab	Local Lab	SST	5mL	5	—	—	—	—	—	—	—	—	—	—	—	—	—	—	—	5			
PPD	?	?	—	Injection	—	—	—	—	—	—	—	—	—	—	—	—	—	X	X	X	0			
Safety labs																								
CBC/Diff/ platelets	Local lab	Local lab	EDTA	5mL	5	—	—	—	—	—	—	—	—	—	—	—	—	—	—	—	5			
Chemistry panel ⁵	Local lab	Local lab	SST	5mL	5	—	—	—	—	—	—	—	—	—	—	—	—	—	—	—	5			
STI Serology																								
Syphilis	Local Lab	Local Lab	SST	5mL	5	—	—	—	—	—	—	—	—	—	—	—	—	—	—	—	5			
Immunogenicity & Mycobacteria assays																								
HLA host genetics	CSR	FHCRC	ACD	8.5mL	—	—	—	—	—	—	—	—	—	—	—	—	—	—	—	—	0			
Cellular assays																								
ICS/ELISPOT / additional tests	CSR	FHCRC	ACD	8.5mL	—	51	—	—	—	—	—	—	51	—	51	51	51	—	—	51	306			
Humoral assays																								
Ab Assays / additional tests	CSR	?	SST	8.5mL	—	17	—	—	—	—	—	—	17	—	17	17	17	—	—	17	102			
Mycobacteria assays																								
BCG PCR	CSR	UW	—		—	—	—	—	—	X	—	—	X	X	X	—	—	—	—	—	0			
BCG Invitro Culture	CSR	CIDR	—	Biopsy	—	—	—	—	—	X	—	—	X	X	X	—	—	—	—	—	0			
Innate Immunity																								
Serum Cytokines	CSR	?	SST	3.5mL	—	3.5	3.5	3.5	3.5	3.5	3.5	3.5	—	—	3.5	3.5	3.5	3.5	3.5	—	35			
Whole Blood Gene Expression	CSR	?	Tempus	3mL	—	3	3	3	3	3	3	3	—	—	3	3	3	3	3	—	30			
STORAGE																								
PBMC	CSR	FHCRC	ACD	8.5mL	—	40	—	—	—	—	—	—	—	—	50	20	20	20	—	—	70	220		
Visit total						29	114.5	6.5	6.5	6.5	6.5	6.5	—	—	74.5	56.5	94.5	94.5	94.5	4	0	4	138	730
56-Day total						29	143.5	150	156.5	163	169.5	—	—	244	300.5	395	489.5	283.5	193	193	197	240.5		
URINE COLLECTION																								
Urinalysis	Local lab	Local lab				X	—	—	—	—	—	—	—	—	—	—	—	—	—	—	—			
Pregnancy test	Local lab	Local lab				X	—	—	—	—	—	—	—	—	—	—	—	—	—	—	—			
Chlamydia/Gonorrhea	Local lab	Local lab				X	—	—	—	—	—	—	—	—	—	—	—	—	—	—	—			

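### Laboratory adverse events are a listed safety outcome, but the five tests behind them are scheduled only at screening

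*Combined protocol and SAP*

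**What the plan says.** Section 15.1 lists what safety is judged on, by frequency and severity. Item 5 reads "Clinical safety laboratory adverse events to include WBC, hemoglobin, and platelet count, creatinine and ALT (SGPT". Tables 6 and 7 in Section 15.2.3 define Grades 1 to 3 for each of these analytes. Section 15.2.1 makes a laboratory abnormality reportable as an adverse event (AE): "An AE can therefore be any unfavorable and unintended sign (including an abnormal laboratory finding".

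On timing, Section 10.6.4 says that blood for these tests "will be collected from each subject prior to administration of Tice® BCG at the screening visit (visit 1". For the rest of the study it adds only: "Additional clinical safety laboratory evaluations may be deemed necessary during the study". Appendix A agrees: the row "CBC/Diff/ platelets" and the chemistry row each carry one 5 mL tube, at screening, with a row total of 5 mL. Section 10.6.4 does schedule "clinical testing for acute phase reactants (ESR and CRP" after dosing, but these are not item 5 analytes and have no grading table.

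Section 18.1 states "All participants are expected to provide safety data" and, for a true event rate of 25% in a group of five, that "there will be a 76% chance of observing at least one event".

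On vital signs, Table 4 grades temperature, pulse and blood pressure, and its footnote takes Day 1 as baseline. BCG is given on Day 0. Section 11.2 and Appendix B list clinic vital signs at screening only.

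**The concern.** The first primary objective is the safety and tolerability of BCG followed by INH, and Section 5.8.1 names hepatitis among the INH risks. A frequency of laboratory AEs needs a known number of people tested after dosing. As scheduled, that number could be anything from none to all, depending on who happens to be tested for cause.

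Symptomatic events are not the problem: health status and AEs are reviewed at every follow-up visit, so symptomatic hepatitis would be looked for. The gap is asymptomatic change in ALT, creatinine or blood counts. A report of no laboratory AEs might then mean that none occurred, or that nobody was tested. The same gap reaches the Section 13.1 endpoint (AEs related to BCG), because an abnormality has to be found before its relatedness can be judged.

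**Working it through.** **1. The plan's own safety figures.** Inputs from Section 18.1: 5 per group, true rate 25%.
- Pr(at least 1 of 5) = 1 - 0.75^5 = 1 - 0.2373 = 0.763; the plan gives 76%.
- Pr(at least 2 of 5) = 1 - 0.2373 - 5 × 0.25 × 0.75^4 = 1 - 0.2373 - 0.3955 = 0.367; the plan gives 37%.

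Both reproduce. They are correct for an event that is looked for in all five participants.

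**2. Is a post-dose safety tube hidden in Appendix A?** Summing the tubes by visit (mL):

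| Visit | Tubes | Total |
|---|---|---|
| Screening | 4 + 5 + 5 + 5 + 5 + 5 (includes CBC 5, chemistry 5) | 29 |
| Day 0 | 51 + 17 + 3.5 + 3 + 40 | 114.5 |
| Days 1, 2, 3, 4 | 3.5 + 3 each | 6.5 each |
| Day 8 | 51 + 17 + 3.5 + 3 | 74.5 |
| Day 15 | 3.5 + 3 + 50 | 56.5 |
| Days 28, 56, 84 | 51 + 17 + 3.5 + 3 + 20 each | 94.5 each |
| Days 98, 112 | 4 each | 4 each |
| Day 114 | 51 + 17 + 70 | 138 |

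Sum: 29 + 114.5 + 4 × 6.5 + 74.5 + 56.5 + 3 × 94.5 + 2 × 4 + 138 = 730, the stated total. No dedicated CBC or chemistry tube is listed after screening. ESR and CRP have no row either, so the table does not rule out running ALT and creatinine on serum drawn for another purpose; it shows only that this is not planned.

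**3. How many draws could have carried the tests?**
- After BCG: Days 1, 2, 3, 4, 8, 15, 28, 56, 84, 98, 112, 114 = 12 draws; item 5 tests scheduled at 0.
- After the last INH dose (Day 6): Days 8, 15, 28, 56, 84, 98, 112, 114 = 8 draws; scheduled at 0.
- Of those, within the Day 56 limit for AE documentation (Section 15.3): Days 8, 15, 28, 56 = 4 draws; scheduled at 0.
- For comparison, ESR and CRP after BCG: Days 1, 2, 3, 4, 8, 15, 28, 56, 84 = 9 days.

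**4. What complete testing would buy.** With 0 events in 5 tested, the exact two-sided 95% upper limit is 1 - 0.025^(1/5) = 0.522, or 52%. Testing everyone gives the zero a meaning; it does not make it precise.

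**5. Vital signs, side by side.** The baseline day in Table 4 (Day 1) falls one day after the injection (Day 0, Section 11.2). Neither Section 11.2 nor Appendix B schedules clinic vital signs on Day 1. Section 10.6.1 could be read as adding a set at the final visit, which would not serve as a baseline. Temperature after dosing is self-recorded and optional (Section 10.6.2).

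**The case against.** The strongest reply is that for-cause testing is the intended design. Item 5 names laboratory AEs without promising a testing schedule. Section 10.6.4 allows extra tests, Section 15.2.5 says how abnormal values are to be handled, and Tables 6 and 7 would be needed to grade any result. Section 16.0 describes licensed products used within labelling, and INH is given for only three days. This is a coherent design, and the choice is a clinical one for the study team. It does not, however, yield a frequency, which is what Section 15.1 says safety is judged on; the text would still have to change.

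It is also fair to say that one Day 8±1 draw, 1 to 3 days after the last INH dose, would miss earlier transient changes and later ones. That stands.

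Four stronger readings are tempting, and the documents do not support them:
- *That the detection chances in Section 18.1 are wrong, or shrink by a known amount.* They reproduce exactly and are given for a generic safety event. Any reduced figure would need an assumed share of participants tested, which the documents do not give.
- *That untested participants will be counted as event-free.* The plan sets no denominator for laboratory AEs, so this is a risk and not a stated rule.
- *That the Day 1 baseline causes events to be missed.* A baseline label does not do that. Table 4 grades on absolute cut-offs, and no change-from-baseline analysis is specified.
- *That nothing is checked just before BCG.* Exclusion 2 implies a physical examination on the day of injection, and exclusion 36 a temperature criterion within the three days before it. What is missing is a scheduled pulse and blood-pressure reading on Day 0.

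**Conclusion.** The point holds. Followed as written, the plan cannot deliver the laboratory part of its own safety assessment: the five analytes are scheduled at 0 of 12 post-BCG draws, and later testing is discretionary. Asymptomatic changes after BCG and INH are not systematically sought, and a zero could reflect not testing. This rests on reading the schedules in Section 10.6.4, Section 11.2 and Appendix A together; they agree, and the tube volumes account for the full 730 mL.

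The size of the problem is that count of missing measurements. It should not be expressed as a loss in detection probability, and no figure in Section 18.1 needs correcting. Symptomatic events remain covered by the AE review.

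The vital-sign baseline is a separate and lesser error: the named day is after dosing and has no scheduled clinic reading, but grading on absolute cut-offs limits the consequence.

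**What to change.** **Preferred.** Add CBC, creatinine and ALT to the existing Day 8 draw in both groups, and report each laboratory AE rate over the number of participants actually tested.

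Cost per participant: 5 mL for the CBC tube, plus 5 mL for chemistry unless ALT and creatinine can be run on serum already drawn (an assumption for the laboratory to confirm).
- Day 8 visit: 74.5 + 5 to 10 = 79.5 to 84.5 mL.
- Appendix A's 56-day total at Day 56: 489.5 + 5 to 10 = 494.5 to 499.5 mL. The row is a rolling volume (it falls to 283.5 mL at Day 84), and the documents state no cap.
- Study total: 730 + 5 to 10 = 735 to 740 mL.
- 10 CBCs and 10 chemistry panels across the trial; no price is given. No new visit.

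**If for-cause testing is intended.** Remove laboratory AEs from the Section 15.1 frequency outcomes, keep Tables 6 and 7 for grading whatever is found, and state in the protocol and report that laboratory safety was not systematically assessed. This costs text edits only.

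**Separately.** Replace the Table 4 footnote so that baseline is the last value before BCG, and record temperature, pulse and blood pressure before BCG on Day 0 and at existing follow-up visits. This needs staff time at visits already planned.
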